#### 11.4.5 Interim an alyses

No interim analysis is planned according the test design.

#### 11.4.6 Safety analysis

Safety analysis is foreseen to be accomplished with the AEs reported by the participants during the trial. Clinical judgement from the PI will be used for the safety evaluation.

#### 11.4.7 Deviation(s) from the original stat istical plan

Any deviation from the original protocol has to be justified and reported in the final report. Post hoc analysis can be done on secondary outcomes and reported in the final report.

#### 11.4.8 Further uses of data

Data collected from the study will potentially be used for further research purposes. The data will remain anonymized and stored in a secure document management system. The participant code list will be destroyed so that nobody will be able to connect the data to a specific test participant.

### 11.5 Handling of missing data and drop -outs

For missing data, the PI will contact the involved subject to evaluate the possibility of getting missing data from a questionnaire by post. If a test subject cannot come to the evaluation visit, after exhausting all the possibilities to reschedule a new one, the devices will be sent back per post. If a subject does not want to adhere to the protocol, he can easily withdraw from the study and return the devices.

Data will be immediately removed if the PI has some doubts about the data accuracy (especially about the understanding of the questionnaires).

Dropouts will not be replaced; therefore, extra subjects over the calculated sample amount will be included from the beginning to ensure enough completed cases with all data.

Analysis will be done on the complete case only.

### 12. QUALITY ASSURANCE AND CONTROL

The Sponsor is responsible for implementing and maintaining quality assurance and quality control systems with written SOPs and working instructions, at all sites. The PI is responsible for proper training of all involved study personnel.

### 12.1 Data handling a nd record k eeping / archiving

Data will be documented on paper and archived with an electronic data management system. The subjects will be given numbers to maintain anonymity. There are also hard copies of subjects' charts that are kept in a locked file cabinet inside of the clinic rooms. Only the PI, statistician, Monitor, and Auditor will have access to the information. The information will always be archived under the identification number with a key to the identification codes stored in another location (described in chapter 2.8).

#### 12.1.1 Case Report Forms

Participant identities are coded using a participant identification number.

The PI or the Site Investigator will enter protocol defined data into a web based Electronic Case Report Forms using an EDC-software that conforms to 21 CFR Part 11 (FDA guidance) requirements. Site staff will be given access to the EDC system after a training. The data are checked automatically for plausibility and discrepancies. The generated appropriate error messages, allow the data to be confirmed or corrected before being saved in the database. At the end of the study, the PI must certify that the data entered into the Electronic Case Report Forms are complete and accurate. After database lock, the PI will receive a CD-ROM or paper copies of the patient data for archiving at the sites.

Field	Author
Date of examination	PI
Participant identification number	PI
Age	PI
Sex	PI
Date of Informed Consent	PI
Inclusion / Exclusion Criteria	PI
Ear disease	PI
Control hearing device serial numbers	PI
Investigational device serial numbers	PI
Results to FST	PI
Results from Gothenburg questionnaire	PI
Results from IOI-HA questionnaire	PI
Results from preference questionnaire	PI
Results from product questionnaire	PI
Results from packaging questionnaire	PI
AEs / SAEs, ADE / SADE	PI
Name, date, signature of PI	PI

The CRF contains the following information:

#### 12.1.2 Specification of source documents

The Principle Investigator will maintain adequate and accurate records to enable the conduction of the study to be fully documented and the study data to be subsequently verified. These documents will be classified into two different categories: PI's file, and subject clinical source documents. There will be a PI file or Ivestigator Site File (ISF) for each site (Bern and Thun) as well as corresponding subject files with source documents pertaining to each site.

The PI's file will contain the CIP/amendments, IB/Instructions for use, CRFs, sites' standard operation procedures (SOPs) or reference to it, EC and CA approval with correspondence, informed consent, device records, staff curriculum vitae and authorization forms, screening and enrolment logs, site-specific subject identification code logs, and other appropriate documents/ correspondence as required by EN ISO 14155 and local regulations.

Subject clinical source documents include, but are not limited to subject hospital/clinic records, physician's and nurse's notes, appointment book, original laboratory reports, CT, X-ray, MRIs, pathology and special assessment reports, consultant letters, etc.

These two categories of documents must be kept on file by the PI for 10 years. If source documents are not durable as long as needed they must be preserved as a copy. When source documents are required for the continued care of the subject, appropriate copies should be made for storing outside of the site. The information will always be archived under the identification number with a key to the identification codes stored in another location (described in chapter 2.8).

For each subject enrolled an encoded electronic CRF must be completed and e-signed by the PI. This also applies to those subjects who fail to complete the study. If a subject withdraws from the study, the reason must be noted on the CRF.

Case report forms are to be completed after the visit.

CRF entries and corrections will only be performed by study site staff, authorized by the PI. All forms should be completed using a blue permanent pen and must be legible. Errors should be crossed out but not obliterated, the correction inserted, and the change initialled and dated by the PI, co-PI or study nurse.

The entries will be checked by the Monitor and any errors or inconsistencies will be checked immediately. The Sponsor-Investigator will collect original completed and signed CRFs at the end of the study. A copy of the completed and signed CRFs will remain on site.

#### 12.1.3 Record keeping / archiving

All study data will be archived for a minimum of 10 years after study termination or premature termination of the clinical trial.

#### 12.2 Data management

#### 12.2.1 Data Management System

The CRFs in this trial are implemented electronically using a dedicated electronic data capturing (EDC) system. The EDC system is activated for the trial only after successfully passing a test procedure.

All data entered in the CRFs are stored on a Windows server in a dedicated database.

#### 12.2.2 Data securit y, access and back-up

The server hosting the EDC system and the database is kept in a locked server-room in Biel. Only the system administrators have direct access to the server. A role concept with personal passwords (site investigator, statistician, monitor, administrator etc.) regulates permission for each user to use the system and database as he/she requires.

All data entered into the CRFs are transferred to the database using Secure Sockets Layer (SSL) encryption. Each data point has attributes attached to it identifying the user who entered it with the exact time and date. Retrospective alterations of data in the database are recorded in an audit table. Time, table, data field, original value and altered value, and the person are recorded (audit trail).

A multi-level back-up system is implemented. Back-ups of the whole system including the database are run several times per day. The back-up-data are stored in a secure place on a different storage-server.

#### 12.2.3 Analysis and archiving

At final analysis, data files will be extracted from the database into statistical packages to be analyzed. The database will be locked at this time, recorded in special archiving format and securely stored for at least 1 year. In addition, the PI will receive a CD-ROM or paper copies of the patient data for archiving at the site.

#### 12.2.4 Electronic and central data validation

Data can be entered into the database only after a check of completeness and plausibility. Furthermore, selected data points are cross-checked for plausibility with previously entered data for that participant.

#### 12.3 Monitoring

The study sites will be monitored by an employee of the Sponsor. A minimum of five visits will be performed; one site initiation visit, 3 routine monitoring visits and one close out visit. The number of routine monitoring visits will be increased if needed based on the course of the study. The first routine monitoring visit will take place shortly after the first patient has been enrolled.

Source documents will be made available for the monitor and the principle investigator or a delegated and authorized person will be available during the visits to answer questions.

100% source data verification will be completed for 3 patients at the first interim visit. For another 3 patients 100% source data verification will be completed at the second interim visit, and an additional 3 at the third interim visit.

Subject to SDV for all patients are:

Patient Informed Consent Form

Eligibility criteria

Diagnosis

Visit dates

Study intervention details related to:

- Procedural success
- Procedure date and time
- (Serious) Adverse Events

Device deficiencies

The content of Investigator Site File (ISF) will be checked during each monitoring visit.

#### 12.4 Audits and Inspections

CEC as well as CA have the right to execute inspections at the study sites.

The study documentation and the source data/documents have to be made accessible to auditors/inspectors and questions have to be answered during audits/inspections. All involved parties must keep the participant data strictly confidential.

### 12.5 Confidentiality, Data Protection

Direct access to source documents will be permitted for the purposes of monitoring, audits and inspections and only authorized persons involved in those activities are allowed to have direct access to source documents and must keep participants data strictly confidential.

#### 12.6 Storage of biologic al material and related health data

Not applicable

### 13. PUBLICATION AND DISSEMINATION POLICY

Trial results will be communicated to participants at the end of the trial. The trial results primary purpose are for internal product validation to ensure safety and performance of the device. The results will be communicated to other relevant groups (e.g., via publication, reporting in results databases, and other internal data sharing arrangements) as needed and for the purpose of sharing scientific information within the industry. The only people with authorship eligibility will be those that worked on the trial including the PI, statistician, and any other clinicians involved in testing. Any plans for writing will not include access to the full protocol but a description of it as well as a description of the participants. Statistics will be described sufficiently so that the reader understands the analysis and any conclusions made from it. Ultimately the decision to submit the report for publication and the ultimate authority over any of the activities is held by the Sponsor, Bernafon.

### 14. FUNDING AND SUPPORT

#### 14.1 Funding

The Sponsor will financially support the trial including providing the clinic and all materials needed to complete the testing. This includes the devices themselves as well as equipment.

### 15. INSURANCE

Insurance will be provided by the Sponsor. A copy of the certificate is filed in each investigator site file and the trial master file.

# 17. APPENDICES

- 1. IMD: IB or SPC
- 2. Medical Devices: IB (according to ISO 14155)
- 3. Medical Devices: Assurance of producer
- 4. Medical Devices: List of norms (vollständig eingehaltene, teilweise eingehaltene)
- 5. Case Report Form (e.g. CRF)
- 6. Patient Information and informed consent
- 7. Instructions for Use
- 8. Meta-Analysis

4.2 Analysis tools	
5. References	8

This test will compared two fitting procedures and devices with the following label:

- Reference Medical Device (RMD): marketed Bernafon device fitted with standardized clinical procedure,
- Investigational Medical Device (IMD): new fitting procedure and device.

While both devices will have the same electro-acoustical performances, it is suspected that changing fitting procedure might influence the subjective benefit for hearing aid user. Research suggest that placebo effect might impact hearing aid trials (Dawes et al., 2013) and that clinician behavior might also modify the perceived benefit of hearing aids (Naylor et al., 2015). The designed test will investigate the potential effect of the IMD compared to the RMD on first time users.

1. Test Design

As the fitting procedure is part of the investigation, no true blinding can be hold. However, the participants will not be told that there is no electro-acoustical difference between IMD and RMD. A balanced cross-over design will be used to guarantee control for period or learning effect. Repeated measures will be analyzed as it reduces the sample size needed to achieve the same test power. No wash out period is needed as it could not be demonstrated that amplification from hearing aid induces a carry-over effect.

1.1 Research question

The test should answer following research questions:

- 1. Narrative effect of fitting procedure: are different fitting procedures leading to differences in perceived benefit with hearing aids despite similar electro-acoustical performances? (Questionnaires)
- 2. Self-administrated audiometry: is AMTAS self-administrated audiometry equivalent to standard clinical procedure? (hearing loss thresholds)

1.2 Timeline

The participants will be randomly allocated into two groups that will have to test the IMD and RMD. Both groups will differ based on test order:

- Group A: IMD for one week and then RMD for one week,
- Group B: RMD for one week and then IMD for one week.

1.3 Random effect

Standardized fitting process is not a homogeneous concept and we expect to have a potential investigator effect that can influence the outcomes. Investigator can be included in the analysis as a fixed or random effect as described by Feaster et al. (2011). As balance between investigators is complicate to hold in practice and limits the generalizability of the results, we will include investigator as a random effect. Feaster et al. (2011) recommends a minimum of 4 investigators trials with site or investigator as random effect. An investigator-by-treatment interaction terms will also be included in the model as recommended by Kraemer and Robinson (2005).

2. Outcomes

2.1 Primary outcomes

The perceived benefit will be measured with:

- a. the IOI-HA questionnaire and its official translation into German (Cox et al., 2002)
- b. a custom questionnaire based on reference article from Naylor et al. (2015).

These two questionnaires were used in the reference article from Naylor et al. (2015) to measure the effect of narrative embodied in the hearing aid fitting process. Even current research question addresses another aspect of the fitting process, these tools have shown a potential to detect changes in the investigated processes.

IOI-HA questionnaire

Perceived benefit of amplification assessed with 7 questions on a 5 points scale (maximum score 35). Indication from reference study found an effect of fitting process between the preferred and less preferred possibility:

- significant 3.2 scale points and an effect size of 0.68 with experience hearing aid users (n = 24),
- non-significant 0.5 scale points with first time hearing aid users (n = 16).

Custom questionnaire

From the reference study, the questionnaire will directly ask about the preference (much better/slightly better/no difference), the certainty of preference (10 points VAS), and the reason (multiple choice: sound quality, speech intelligibility, listening effort, comfort, loudness, other).

- Fitting procedures: no significant difference between both fitting procedures for first time and experienced hearing aid users,
- Placebo effect: 20 out of 24 indicated a difference with a mean certainty of 7.9/10 for the experienced users group. 14 out of 16 indicated a difference with a mean certainty of 7.0/10 for the first time users group

Order effect

From the reference study, test order might play a different role for first time or experienced users:

- No order effect was found with the experienced hearing aid users,
- A highly significant test order effect in favor for the second tested hearing aid was found for the first time users.

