### 7.1 Eligibil ity criteria

Participants fulfilling all of the following inclusion criteria are eligible for the study:

- All classifications of hearing loss (sensorineural, conductive, combined)
- If the hearing loss is conductive or combined it must be approved for amplification by a physician
- All shapes of hearing loss (flat, sloping, reverse slope, notch)
- Hearing loss severity ranging from mild to severe
- First time hearing aid users
- German speaking
- Both genders
- Ages 18 and older
- Ability and willingness to sign the consent form

The presence of any one of the following exclusion criteria will lead to exclusion of the participant:

- Contraindications for amplification
- Experienced or current hearing aid users
- Active ear disease
- Inability to follow the procedures of the study due to language problems, psychological disorders, dementia, or other cognitive problems of the participant,
- A reduced mobility making them unable to attend weekly study appointments
- A reduced ability to describe auditory impressions and the usage of the hearing aids
- Uncooperative so that it is not possible to record a valid pure tone audiogram
- A strongly reduced dexterity
- Central hearing disorders
- Bernafon employees
- Family members of Bernafon employees

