### 8.4 Compliance with study intervention

It is clearly explained to the subjects that during the periods of intervention it is important to the study that they wear the hearing aids. However, it is the responsibility of the subject to place the hearing aids in their ears every morning.

The software monitors the amount of time that the devices are worn. Therefore, it will be noted if the hearing aids from either field trial have not been worn the expected amount of time or if the time worn between trial periods is not similar. If the device has not been worn a sufficient amount of time the data will not be used for the study. The subjects will be asked to return the devices.

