### 11.4 Planned Analyses

The analysis and documentation will be done by the statistician using R (latest available and validated version) downloaded from the official Comprehensive R Archive Network (https://cran.r-project.org/). R-Studio IDE will be used to integrate the analysis to the report. R provides adequate packages for descriptive statistics (base, stats, and Rmisc), data visualisation (ggplot2), mixed effect models (Imer, ImerTest, and nIme), and principal component analysis (FactoMineR).

A linear mixed effect regression will be used on the IOI-HA questionnaire, chi-squared distribution on the preference test and a paired t-test on hearing thresholds. The principal component analysis will be made on different outcomes and explanatory variables combinations.

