#### 11.4.2 Primary Analysis

The narrative effect on the subject perception of the end user will be measured using a standardized questionnaire, the IOI-HA, and a custom product questionnaire. The questionnaires will be administered twice during the study, once after each field trial period. The responses for the IMD will be compared with those for the RMD. At the last visit the subjects will complete a preference questionnaire based on the Naylor et al. (2015).

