4.1 Analysis methods

Linear mixed effect regression will be used on the IOI-HA questionnaire, chi2 distribution on the preference test and paired t-test on audiometrical thresholds. Principal component analysis will be made on different outcomes and explanatory variables combinations.

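### The SAP cites a strong second-device effect in first-time users, the only people enrolled, but relies on cross-over balance and names no period term in the IOI-HA mixed model

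*SAP*

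**What the plan says.** - SAP 2.1, under the order effect, reports no such effect in experienced users of the reference study. For first-time users it says: "A highly significant test order effect in favor for the second tested hearing aid was found for the first time users". It gives neither the size nor the outcome.
- Protocol 7.1 lists "First time hearing aid users" as an inclusion criterion and excludes experienced users. Protocol 11.4.1 describes the analysed population the same way.
- SAP section 1 gives the control: "A balanced cross-over design will be used to guarantee control for period or learning effect".
- SAP 1.3 makes investigator a random effect and adds: "An investigator-by-treatment interaction terms will also be included in the model".
- SAP 4.1 says "Linear mixed effect regression will be used on the IOI-HA questionnaire", and protocol 11.4 says the same. Protocol 11.4.2 adds only "The responses for the IMD will be compared with those for the RMD". None of these names period, sequence or test order as a model term.
- Protocol 7.3 uses test order as a two-level randomisation factor but does not carry it into the analysis.
- Protocol 8.4: "If the device has not been worn a sufficient amount of time the data will not be used for the study". Protocol 11.5 restricts the analysis to complete cases and removes data the principal investigator doubts. It also says dropouts are not replaced, whereas protocol 7.4 provides back-up participants to replace withdrawals.

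**The concern.** The plan cites a strong order effect in exactly the population it recruits and then draws no consequence for the analysis. In a two-period cross-over, balance does one thing: if both sequences contribute equally, the period shift cancels from the treatment estimate. It does not remove the shift from the spread of the individual differences, so the interval is wider than it needs to be. If the completing sequences are unequal, part of the shift is also reported as a difference between fitting methods, in either direction.

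This bears on the main question. Protocol 4.2 asks whether the benefit with the IMD is as good as, and not inferior to, that with the RMD. The answer is read from an estimate and its interval.

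**Working it through.** **The plan's own power figures.** Noncentral chi-square with noncentrality n·w², n = 24, alpha 0.05: w = 0.65 on 2 df gives 0.821 (stated 0.82), and w = 0.6 on 1 df gives 0.836 (stated 0.84). Both reproduce. Both concern the preference test; no power is stated for IOI-HA.

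**Inputs, all assumed.**
- SD of the within-person IOI-HA difference: 3.2/0.68 = 4.7. Both figures are in SAP 2.1, but they come from experienced users and a preferred-versus-less-preferred contrast, and the effect size is read as one for paired differences.
- True IMD-RMD effect: 3 points.
- Period shift π in favour of the second device: 0.5, 1.6 or 3.2 points.
- 24 completers, two-sided alpha 0.05.

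**Set-up.** Let d = IMD minus RMD and τ the true effect. The mean of d is τ − π in the IMD-first sequence (n1) and τ + π in the RMD-first sequence (n2).
- Without a period term: one-sample t on all d. Bias = −π(n1 − n2)/(n1 + n2). At balance the variance is inflated by about 1 + π²/SD².
- With a period term: the average of the two sequence means, pooled within-sequence variance, n − 2 df. Unbiased at any split.

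**Variance at 12:12.** 1 + 0.5²/4.7² = 1.01; 1 + 1.6²/4.7² = 1.12; 1 + 3.2²/4.7² = 1.46.

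**Size of the bias.** At 13:11, 2/24 of the shift: 0.04, 0.13, 0.27 points. At 14:10, 4/24 of the shift: 0.08, 0.27, 0.53 points.

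**Simulation, 100,000 trials per cell.** Entries are for shifts 0.5 / 1.6 / 3.2.

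| Split and direction | Power without term | Power with term |
|---|---|---|
| 12:12 | 0.85 / 0.82 / 0.73 | 0.85 |
| 13:11, imbalance opposes the effect | 0.84 / 0.78 / 0.63 | 0.84–0.85 |
| 13:11, imbalance favours it | 0.86 / 0.85 / 0.80 | 0.84–0.85 |
| 14:10, imbalance opposes it | 0.83 / 0.74 / 0.53 | 0.84 |
| 14:10, imbalance favours it | 0.87 / 0.88 / 0.87 | 0.84 |

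Repeat runs agree to within about 0.01. The power in the last row comes from an inflated estimate. The mean 95% half-width at 12:12 is 1.97 / 2.08 / 2.39 points without the term and 1.97 with it. Type I error without the term is 0.02 to 0.05 throughout.

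**How likely is imbalance?** Suppose 28 start at 14:14 and 4 are lost at random (hypergeometric). Completers are 12:12 with probability 0.40, 13:11 either way with 0.50, and 14:10 either way with 0.10.

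**Sensitivity.**
- SD at 12:12, shifts 1.6 / 3.2: SD 3.5 gives power 0.97 / 0.90 against 0.98 with the term; SD 6 gives 0.62 / 0.55 against 0.65.
- True effect 0.5 points, the IOI-HA figure SAP 2.1 cites for first-time users: power is about 0.08 with the term and 0.02 to 0.10 without it, so the term does not rescue that case.
- No period shift: the term costs 0.850 versus 0.848 at 12:12 and 0.848 versus 0.838 at 14:10.

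**The case against.** **Period is unspecified, not ruled out.** The analysis sections give the mixed model one clause and list no fixed effects at all. An analyst could include period. That is true, but the SAP does specify the investigator terms, and where it discusses period it relies on the design. Naming the term now removes a choice that would otherwise be made after the data are seen.

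**The order effect may not concern IOI-HA.** The paragraph follows the preference questionnaire and names no outcome. If the effect was on preference, the 0.5-point IOI-HA contrast cited for first-time users suggests a small shift and a negligible loss at balance. If it was on IOI-HA, p < 0.01 with 16 participants and SD 4.7 would need an observed shift of about 3.5 points (2.95 × 4.7/√16). The documents do not decide between these readings, so the size stays open.

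**The simulated analysis is simpler than the planned model.** It has no investigator terms. If treatment were tested against the investigator-by-treatment interaction on 3 df, power for 3 points would be about 0.56 even with no investigator variance. This stands: the absolute power values may not apply to the final model, and the gain from the period term was not recomputed under it. The bias formula for the simple difference does not depend on this.

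**The study is declared exploratory, and the consequence is limited.** Type I error is not inflated, and the average bias is zero unless loss depends on sequence. Both points are accepted. What remains is precision, and the accuracy of the estimate in the one trial that is run.

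**Conclusion.** The concern holds. The documents cite a strong order effect in first-time users, enrol no one else, rely on balance to control it, and name no period term for IOI-HA. Balance among the analysed participants is not assured.

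The missing term is certain; its cost is not. Under the assumed inputs the cost runs from negligible (0.5-point shift, 12:12) to a fall in power from 0.85 to 0.73 at balance, and to 0.53 with a 0.53-point bias at an adverse 14:10 split (3.2-point shift). None of this makes the trial invalid, and the stated preference-test power is not in dispute. The change should be made because the plan itself cites the risk and the remedy is nearly free.

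**What to change.** In SAP 4.1 and protocol 11.4.2, write out the IOI-HA model: fixed treatment and period, random participant, and investigator and investigator-by-treatment as already planned. Report the period estimate and the number of completers by sequence. In SAP section 1, replace the claim that balance guarantees control with a statement that period is modelled. A fixed sequence term is optional: with complete pairs it does not change the within-participant treatment contrast. Because the order effect may have been on preference, also state how test order is handled in that analysis; a period term for IOI-HA does not cover it.

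For the IOI-HA model the cost is one line in each document and one degree of freedom, about 1 point of power at most at the splits examined if there is no period effect. No visit, procedure or sample size changes.
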